### 6.3.3 Criteria for Rechallenge of Blinatumomab and Other Protocol-required Therapies After Potential Hepatotoxicity

If signs or symptoms recur with rechallenge, then blinatumomab and other protocol-required therapies, as appropriate, should be permanently discontinued.

Subjects who clearly meet the criteria for permanent discontinuation (as described in [Section 6.2.1.4.3](#)) should never be rechallenged.

Approved

## 6.4 Concomitant Therapy

Throughout the study, investigators may prescribe any concomitant medications or treatments deemed necessary to provide adequate supportive care except for those listed in [Section 6.8](#).

For concomitant therapies being taken for NHL and that assist in the evaluation of efficacy or safety endpoints, collect therapy name, indication, dose, unit, frequency, start date and stop date.

For all other concomitant therapies, collect therapy name, indication, dose, unit, frequency, route, start date and stop date.

All treatments that the investigator considers necessary for a subject's welfare may be administered at the discretion of the investigator in keeping with the community standards of medical care. All concomitant medication will be recorded on the CRF including all prescription, over-the-counter, herbal supplements, and IV medications and fluids. Concomitant therapies are to be collected from signing of the informed consent form through the safety follow-up period. For therapies used for the treatment of lymphoma, all data for medications and treatments will be recorded from the time of diagnosis of the lymphoma, not the signing of the informed consent form. If changes occur during the study period, documentation of drug dosage, frequency, route, and date may also be included on the CRF.

## 6.5 Other Treatment Procedures

### 6.5.1 Fever Management

Fevers may be managed per local clinical standard of care. For symptomatic relief of fevers due to any cause (eg, infection, drug fever) the recommended first choices for fever management are paracetamol/acetaminophen and/or dexamethasone. The dexamethasone dose should be reduced step-wise as soon as the fever is resolved. If these are not sufficiently effective, pethidin/meperidine is recommended. For pethidin/meperidine, adequate antiemetic prophylaxis should be administered. The treating physician should also use their clinical judgment to determine the underlying cause of the fever and treatment. For instance, in the case of fever due to infection one should consider the use of antibiotics and avoid the use of dexamethasone.

Approved

## 6.6 Medical Devices

Blinatumomab (cIV) must be administered using infusion pumps approved for use by the appropriate regulatory authorities for the country in which the subject is undergoing treatment.

Blinatumomab infusion for solution will be prepared in bags for IV infusion and delivered through infusion lines that are both compatible with the IP as described in the IPIM. The blinatumomab final solution for infusion should not come into contact with the pump at any time.

SC formulation dosing will be administered via standard, locally available plastic disposable syringe.

Additional details for the use of the above-mentioned medical devices are provided in the IPIM.

## 6.7 Product Complaints

A product complaint is any written, electronic or oral communication that alleges deficiencies related to the identity, quality, durability, reliability, safety, effectiveness, or performance of a drug(s) or device(s) after it is released for distribution to market or clinic by either Amgen or by distributors and partners for whom Amgen manufactures the material.

This includes any drug(s), device(s) or combination product(s) provisioned and/or repackaged /modified by Amgen. Drug(s) or device(s) includes investigational product.

Any product complaint(s) associated with an investigational product(s) or non-investigational product(s) or device(s) supplied by Amgen are to be reported according to the instructions provided in the IPIM.

## 6.8 Excluded Treatments, Medical Devices, and/or Procedures During Study Period

Subjects are prohibited from receiving the following therapies during the Screening and Treatment Phase of this study:

- antineoplastic systemic chemotherapy or biological therapy such as rituximab or obinutuzumab and/or other monoclonal antibody
- immunotherapy not specified in this protocol such as anti-CD19 targeted therapies, chimeric antigen receptor T-cell or other cellular therapies

- investigational agents other than blinatumomab
- radiation therapy including radioimmunotherapy

Exception: Palliative radiation therapy to a symptomatic solitary lesion may be considered. The subject must have clear measurable disease outside the radiated field.

## **6.9 Contraceptive Requirements**

### **6.9.1 Female Subjects**

A female is considered of childbearing potential unless she has undergone a hysterectomy, bilateral salpingectomy, bilateral oophorectomy, or is postmenopausal.

Postmenopausal is defined as:

- A postmenopausal state is defined as no menses for 12 months without an alternative medical cause. (A high follicle stimulating hormone level in the postmenopausal range may be used to confirm a postmenopausal state in women not using hormonal contraception or hormonal replacement therapy [HRT]. However, in the absence of 12 months of amenorrhea, a single follicle stimulating hormone measurement is insufficient).
- Females on HRT and whose menopausal status is in doubt will be required to use one of the non-hormonal highly effective contraception methods if they wish to continue their HRT during the study. Otherwise, they must discontinue HRT to allow confirmation of postmenopausal status before study enrollment.

Female subjects of childbearing potential must agree to practice sexual abstinence or use an acceptable method of effective contraception during the treatment and for an additional 48 hours after the last dose of cIV or **96** hours after the last dose of SC blinatumomab.

Acceptable methods of contraception include:

- Combined (estrogen and progestogen) or Progestogen-only hormonal methods given via oral, intravaginal, transdermal, injectable, or implantable route
- Intrauterine device (IUD)
- Intrauterine hormonal-releasing system (IUS)
- Bilateral tubal ligation/occlusion
- Vasectomized partner (Provided that partner is the sole sexual partner of the female subject of childbearing potential and that the vasectomized partner has received medical assessment of the surgical success)

Approved

- Sexual abstinence (Defined as refraining from heterosexual intercourse during the entire period of risk associated with the study treatments. The reliability of sexual abstinence must be evaluated in relation to the duration of the trial and the preferred and usual lifestyle of the subject.)
- Double barrier method: the male uses a condom and the female may choose either a cervical cap, diaphragm, or contraceptive sponge with spermicide (A female condom is not an option due to the risk of tearing when both partners use a condom.)

Female subjects of childbearing potential must receive pregnancy prevention counseling and be advised of the risk to fetus if they become pregnant during treatment and for an additional 48 hours after the last dose of cIV blinatumomab or **96** hours after the last dose of SC blinatumomab.

Additional medications given during treatment with blinatumomab may alter the contraceptive requirements. These additional medications may require female subjects use highly effective methods of contraception and for an increased length of time. In addition, male subjects may also be required to use contraception. The investigator is to discuss these contraceptive changes with the subject.

If a female subject is suspected of being pregnant, the protocol-required therapies must be stopped immediately and may not be resumed until absence of pregnancy has been medically confirmed.

#### **6.9.2 Unacceptable Methods of Birth Control for Women Subjects**

Birth control methods that are considered unacceptable in clinical trials include: periodic abstinence (calendar, symptothermal, post-ovulation methods), withdrawal (coitus interruptus), spermicides only, and lactational amenorrhea method.

### **7. STUDY PROCEDURES**

Screening assessments and study procedures outlined in this section and in [Table 3](#), [Table 4](#), [Table 5](#), [Table 6](#), and [Table 7](#) will be performed after obtaining a signed informed consent form.

It is very important to attempt to perform study procedures and obtain samples at the precise timepoints stipulated below. When it is not possible to perform the study visit at the exact time point, the visit may be performed within the acceptable visit window as defined in the visit-specific section below.

Any missed visits, tests not done, or examinations that are not conducted must be reported as such on the CRFs. Subsequent study visits should resume on the original

schedule. Missed assessments at prior visits should not be duplicated at subsequent visits.

Refer to the applicable supplemental laboratory manuals for detailed collection and handling procedures.

Approved

7.1 Schedule of Assessments

Table 3. Schedule of Assessments for Cycle 1/Period 1

Study Part	Screening	Treatment Period																				Safety Follow-up a, b, c EOS (+ 7 days)	
		cIV Run-in							Subcutaneous Administration							cIV to complete 6 weeks of treatment				EOT (± 3 days)			
Cycle Day	-14 to -1	1	2	3	8	9	10	15	16	17	22	23	24	25	26	27	28	29	30	31	37	43	
Cycle Week		1			2			3			4							5		6			
GENERAL AND SAFETY ASSESSMENTS																							
Informed consent	X																						
Inclusion/exclusion criteria	X																						
Medical history/ current medical conditions	X																						
Demographics	X																						
ECOG Performance Status	X																						X
Physical examination (including neurologic examination) d	X	X	X	X	X	X	X	X	X	X	X	X	X	X	X	X	X	X	X		X	X	X
Hospitalization e		X	X	X	X	X	X	X	X	X	X	X	X	X	X	X	X	X	X				
Vital signs, temperature f	X	X	X	X	X	X	X	X	X	X	X	X	X	X	X	X	X	X	X	X	X	X	X
Concomitant medications	X	X	X	X	X	X	X	X	X	X	X	X	X	X	X	X	X	X	X	X	X	X	X
Adverse events g		X	X	X	X	X	X	X	X	X	X	X	X	X	X	X	X	X	X	X	X	X	X
Serious adverse events g	X	X	X	X	X	X	X	X	X	X	X	X	X	X	X	X	X	X	X	X	X	X	X
Disease related events		X	X	X	X	X	X	X	X	X	X	X	X	X	X	X	X	X	X	X	X	X	X
LABORATORY ASSESSMENTS																							
Serum or urine pregnancy test h	X																						
Coagulation i	X																						X
Hematology	X	X	X		X	X		X	X		X	X						X	X		X	X	X
Chemistry	X	X	X		X	X		X	X		X	X						X	X		X	X	X
Urinalysis	X																						

Approved

Footnote defined on next page of the table

**Table 3. Schedule of Assessments for Cycle 1/Period 1**

Study Part	Screening	Treatment Period																				Safety Follow-up a, b, c EOS (+ 7 days)			
		cIV Run-in										Subcutaneous Administration								cIV to complete 6 weeks of treatment			EOT (± 3 days)		
		Cycle Day	1	2	3	8	9	10	15	16	17	22	23	24	25	26	27	28	29	30	31		37	43	
Cycle Week	1	2			3			4								5		6							
LABORATORY ASSESSMENTS (Continued)																									
Hepatitis serology, HIV	X																								
Anti-blinatumomab antibody		X p									X p										X p			X	
IgG	X																					X	X		
Lumbar puncture l	X																								
Creatinine Clearance k	X																								
INVESTIGATIONAL PRODUCT DOSING																									
Blinatumomab		X	X	X	X	X	X	X	X	X		—see Table 4 below—													
BIOMARKER ASSESSMENTS																									
Cytokines		X q									X q														
Lymphocyte subsets l		X									X														
PK ASSESSMENTS																									
Blinatumomab PK sample			X r			X r			X r		—see Table 4 below—														
DISEASE ASSESSMENTS																									
PET-CT, CT, or contrast enhanced CT m	X																						X		
Bone marrow biopsy n, o	X																						X s		

Approved

Abbreviations: cIV = continuous intravenous, CRS = cytokine release syndrome, CTCAE = Common Terminology Criteria for Adverse Events, CT = computed tomography, ECOG = Eastern Cooperative Oncology Group, EOT = end of treatment, EOS = end of study, HIV = human immunodeficiency virus, IgG = immunoglobulin G, INR = international normalized ratio, IP = investigational product, PET = positron emission tomography, PK = pharmacokinetic, PTT = partial thromboplastin time, q12h = every 12 hours, SC = subcutaneous.

a If a subject discontinues the study the safety follow-up procedures should be conducted immediately.

b All subjects, including subjects who withdraw from the study early, should complete a safety follow-up visit 30 (+ 7) days after the last dose of blinatumomab, or before hematopoietic stem cell transplant (HSCT) or any other non-protocol specified anti-tumor therapy, if applicable.

c Safety follow-up (EOS) should only be done following cycle 1 if treatment is ended after the 6 weeks of blinatumomab and no second cycle is planned to be administered. If a second cycle is planned then obtain the EOS after cycle 2.

- d Physical examination will include weight. Screening only: medical and surgical history, and height will **also** be obtained. Physical examination should be performed before the start of cIV infusion or dose increase, or before the subcutaneous injection, respectively.
- e Hospitalization during cIV administration in Period 1: at least 72 hours at the start of cIV and after each dose-step, as well as for at least 48 hours after **the return to cIV infusion after the SC dosing in Cycle 1/Period 1**. Hospitalization during subcutaneous administration: 5 days **SC administration**, and an additional 2 days **drug free (7 days total)**. NOTE: SC dosing should begin on a Monday (unless the study site can administer SC injections on the weekend).
- f The investigator should monitor the subject's vital signs continuously every 4 hours ( $\pm$  2 hours) during the first 12 hours after the start of each new treatment/dose-step. Subject must be in a supine position in a rested and calm state for at least 5 minutes before blood pressure assessments are conducted. If the subject is unable to be in the supine position, the subject should be in most recumbent position possible. The position selected for a subject should be the same throughout the study. Vital sign measurements will be repeated daily during the subject's hospitalization.
- g Serious adverse events are collected from the time of signing informed consent form to the end of study and adverse events are collected after the first dose of IP.
- h Serum or urine pregnancy test will be performed for all female subjects unless surgically sterile or > 2 years postmenopausal. Additional pregnancy testing may be performed at the investigators' discretion or as required per local laws and regulations.
- i Coagulation will include partial thromboplastin time (PTT), INR, and fibrinogen.
- j Lumbar puncture is only needed for disease assessment per standard of care per investigator. Lumbar puncture should be obtained for evaluation of seizures during blinatumomab treatment, if clinically stable, and a sample sent for blinatumomab PK.
- k **Creatinine clearance to be calculated by Cockcroft-Gault equation.**
- l Lymphocyte subsets for the study are listed above in SOA and are to be collected prior to administration of IP on days 1 and 22, however, additional samples will be collected for adverse events of CTCAE  $\geq$  grade 3 neuro toxicity and CRS occurs throughout the study at the start and resolution of the event (**refer to Section 7.3.16.1**).
- m Disease assessments are to be performed to establish staging and response per Cheson **if disease assessment is by CT scans (Appendix A)** and Lugano criteria **if disease assessment includes PET/CT (Appendix B)**. For PET-CT, CT, or contrast enhanced CT the same imaging modality should be used throughout the study for an individual subject. Disease assessment to occur: during screening; just prior to optional cycle 2 if given (attempt to obtain this study at least 2 weeks after stopping IP in cycle 1 and just prior to starting cycle 2); and the last disease assessment is 4 weeks after finishing the last dose of IP. If PET and CT are acquired on the same day, it is strongly recommended that PET is performed prior to the CT with IV contrast.
- n Bone marrow biopsy to be performed according to Cheson ([Appendix A](#)) and Lugano criteria ([Appendix B](#) [standard of care per investigator]).
- o Bone marrow biopsy performed within 21 days of the first dose of IP may be used in place of screening assessment to establish staging or response per Cheson ([Appendix A](#)) and Lugano criteria ([Appendix B](#)).
- p Anti-blinatumomab antibody predose on day 1, before the administration of first SC dose (following 12 hour wash out from cIV), and predose at the re-start of cIV infusion (following the 2 to 3 day washout).
- q **Cytokine sample on days 1 and 22: predose and at the following time points postdose, 2 hours ( $\pm$  15 minutes), 4 hours, 6 hours ( $\pm$  30 minutes for both the 4 and 6 hour time points), and 12 hours (before the next injection in case of q12h dosing  $\pm$  1 hour). Additional samples will be collected for adverse events of CTCAE  $\geq$  grade 3 neuro toxicity and CRS occurs throughout the study at the start and resolution of the event (Refer to [Section 7.3.16.2](#)).**
- r During cIV run-in, PK samples are collected any time during the day on the second day after the start of the 9  $\mu$ g/day, 28  $\mu$ g/day and 112  $\mu$ g/day doses, (obtain samples on days 2, 9, and 16, respectively). During SC dosing, PK samples are collected per [Table 4](#). Refer [Section 7.3.15](#) for detail, sampling window and handling if dose interruption occurred. Additional samples will be collected for adverse events of CTCAE  $\geq$  grade 3 neuro toxicity and CRS occurs throughout the study at the start of the event, 24 hours after the event, and at the resolution of the event (Refer to [Section 7.3.15](#)).
- s Bone marrow biopsy only to be repeated with a response assessment (~3 weeks after end of treatment as per standard of care) to establish staging or response per Cheson ([Appendix A](#)) and Lugano criteria ([Appendix B](#)).

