- k Disease assessments are to be performed as to establish staging and response per Cheson (Appendix A) and Lugano criteria (Appendix B). For PET-CT, CT, or contrast enhanced CT the same imaging modality should be used throughout the study for an individual subject. Disease assessment to occur: during screening; just prior to optional cycle 2 if given (attempt to obtain this study at least 2 weeks after stopping IP in cycle 1 and just prior to starting cycle 2); and the last disease assessment is 4 weeks after finishing the last dose of IP. If PET and CT are acquired on the same day, it is strongly recommended that PET is performed prior to the CT with IV contrast.
- l Bone marrow biopsy to be performed according to Cheson (Appendix A) and Lugano criteria (Appendix B [standard of care per investigator]).
- m Bone marrow assessment performed within 21 days of the first dose of IP may be used in place of screening assessment to establish staging or response per Cheson (Appendix A) and Lugano criteria (Appendix B).
- n Anti-blinatumomab antibody on day 1 predose
- o Cytokines will be obtained as outlined in the dosing option tables (Table 6); additional cytokine samples will also be collected for adverse events of CTCAE ≥ grade 3 of CRS or neurotoxicity if it occurs (Refer to Section 7.3.16.2). Obtain the samples as close as possible to the start of the event and at resolution of the event (Refer to Section 7.3.16.2).
- p Lymphocyte subsets will be collected as outlined in the dosing option tables (Table 6) additional samples will be collected for adverse events of CTCAE ≥ grade 3 neuro toxicity at the start and resolution of the event (Refer to Section 7.3.16.1).
- q The PK samples will be obtained as outlined in the dosing options table (Table 6). (Refer to Section 7.3.15.2 for sampling times, sampling window and handling for dose interruption). PK data will also be collected in the events of CTCAE ≥ grade 3 adverse events of CRS or neurotoxicity that occurs during SC administration. Obtain the samples as close as possible to the start of the event, at approximately 24 hours after the event, and at the end of the event when all symptoms are resolved (refer to Section 7.3.15.2).

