g Serum or urine pregnancy test, prior to starting IP on day 1, will be performed for all women subjects unless surgically sterile or > 2 years postmenopausal. Additional pregnancy testing may be performed at the investigator's discretion or as required per local laws and regulations.

h Coagulation will include PTT, INR, and fibrinogen.

i Disease assessments are to be performed to establish staging and response per Cheson ([Appendix A](#)) and Lugano criteria ([Appendix B](#)). For PET-CT, CT, or contrast enhanced CT the same imaging modality should be used throughout the study for an individual subject. If PET and CT are acquired on the same day, it is strongly recommended that PET is performed prior to the CT with IV contrast. Obtain assessments prior to starting cycle 2 blinatumomab and also at the EOS safety follow-up.

j Bone marrow biopsy is not required if PET scan is negative and if not otherwise clinically necessary by investigator discretion. If bone marrow biopsy is needed, obtain just prior to cycle 2 and repeat at the EOS safety follow-up.

k Anti-blinatumomab antibody on day 1 pre-dose.

l Bone marrow biopsy only to be repeated with a response assessment (~ 3 weeks after end of treatment as per standard of care) to establish staging or response per Cheson ([Appendix A](#)) and Lugano criteria ([Appendix B](#)).

m **Assessments/Laboratory studies for optional cycle 2/Period 1 or option cycle 2/Period 2 if administered as cIV infusion should be obtained Days 1, 2 (week 1), 8, 9 (week 2), 15, 16 (week 3), and days 22, 29, 36 and EOT D43 ( $\pm$  3 days). Assessments/Laboratory studies for optional cycle 2/period 2 if administered SC should be obtained on Days 1, 2, and 3 (week 1), Days 8 and 12 (week 2) for q48h, q72h, q96h and q7 day dosing options; Only obtain Day 14 (week 2) for q48h dosing option, Only obtain Day 15 (week 3) for q72h dosing option; Only obtain Day 16 (week 3) for q 48h and q96H dosing option; Only obtain Day 19 (week 3) for q7day dosing option. All dosing options will have the EOT D43 ( $\pm$  3 days) assessments/laboratory studies.**

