### Appendix A. Modified Cheson Criteria for Evaluation of Extramedullary Disease

Response	Definition	Nodal Masses	Spleen, Liver	Bone Marrow
CR	Disappearance of all evidence of disease	(a) FDG-avid or PET positive prior to therapy; mass of any size permitted if PET negative  (b) Variably FDG-avid or PET negative; regression to normal size on CT	Not palpable, nodules disappeared	Infiltrate cleared on repeat biopsy; if indeterminate by morphology, immunohistochemistry should be negative
PR	Regression of measurable disease and no new sites	≥ 50% decrease in SPD of up to 6 largest dominant masses; no increase in size of other nodes  (a) FDG-avid or PET positive prior to therapy; one or more PET positive at previously involved site  (b) Variably FDG-avid or PET negative; regression on CT	≥ 50% decrease in SPD of nodules (for single nodule in greatest transverse diameter); no increase in size of liver or spleen	Irrelevant if positive prior to therapy; cell type should be specified
SD	Failure to attain CR/PR or PD	
 
FDG-avid or PET positive prior to therapy; PET positive at prior sites of disease and no new sites on CT or PET
 
Variably FDG-avid or PET negative; no change in size of previous lesions on CT
 
		
Relapsed disease or PD	Any new lesion or increase by ≥ 50% of previously involved sites from nadir	Appearance of a new lesion(s) > 1.5 cm in any axis, ≥ 50% increase in SPD of more than one node, or ≥ 50% increase in longest diameter of a previously identified node > 1 cm in short axis  Lesions PET positive if FDG-avid lymphoma or PET positive prior to therapy	> 50% increase from nadir in the SPD of any previous lesions	New or recurrent involvement

Abbreviations: CR, complete remission; FDG, [F]fluorodeoxyglucose; PET, positron emission tomography; CT, computed tomography; PR, partial remission; SPD, sum of the product of the diameters; SD, stable disease; PD, progressive disease.

Approved

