10.6.1 Analyses of Secondary Efficacy Endpoint(s)

The efficacy endpoint of the study is ORR (CR+PR) after blinatumomab treatment based on [Chesons' 2007](#) criteria ([Appendix B](#)). The analysis is based on the response evaluation recorded in the CRF for subjects in the full analysis set. Subjects will be considered as non-responders if there is no response assessment available. The rate will be estimated along with its 95% Clopper-Pearson exact confidence interval by dose group and overall. Subject listings with related collected parameters will also be provided.

Summary of other best responses status by each response category will be also provided. The number and percentage of subjects with a disease response of complete response (CR), partial response (PR), stable disease (SD) or progressive disease (PD) will be presented for the dose escalation and/or expansion parts of the study.

Subject listings with related collected parameters will also be provided.

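### Table 3 footnote m ties the response criteria to imaging modality in Period 1, so PET/CT subjects may have no Cheson category for the Cheson-based secondary ORR

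*Protocol*

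**What the plan says.** **Endpoint and analysis.** Protocol Section 10.1.1.2 and SAP Section 4.1.2 define the secondary ORR as CR plus PR by best overall response under Cheson. Protocol Section 10.4.2 and SAP Section 10.6.1 analyse it in the full analysis set from the response entered in the CRF. SAP 10.6.1 adds an exact 95% interval by dose group and overall. Neither document limits this endpoint to subjects imaged by CT. Lugano ORR is exploratory.

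**Period 1 schedule.** Table 3 footnote m attaches a condition to each set of criteria: Cheson applies "if disease assessment is by CT scans (Appendix A") and Lugano applies "if disease assessment includes PET/CT (Appendix B"). It also says that "the same imaging modality should be used throughout the study for an individual subject".

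**Other places.** For Period 2, Table 5 footnote k asks for assessments "to establish staging and response per Cheson (Appendix A) and Lugano criteria (Appendix B"), with no modality condition. Table 7 footnote i does the same for optional Cycle 2. Protocol Section 7.3.10 cites both appendices, and the definition of best overall response in SAP Section 6 names both criteria.

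**Missing responses.** SAP 10.6.1 states: "Subjects will be considered as non-responders if there is no response assessment available". It does not say under which criteria the assessment must be missing. SAP Section 11 declares no changes from the protocol-specified analyses.

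**The concern.** The endpoint needs a Cheson category for every treated subject, but the Period 1 schedule, read on its own, asks for one only when imaging is by CT. Because a subject stays on one modality, a PET/CT subject would have no later CT-only assessment to supply it. Protocol Section 7.3.12 rules out central reads, so the site's entry is the only source.

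A subject with only a Lugano category could be handled in three ways, and the SAP chooses none of them:

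- **Count as a non-responder.** The ORR falls with the PET/CT share, whatever the drug does.
- **Use the Lugano category.** The rate labelled Cheson mixes two sets of criteria and partly merges with the exploratory endpoint.
- **Exclude.** The denominator is no longer the full analysis set.

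Period 2 has no such condition in its schedule. If Period 1 alone is affected, the Period 1, Period 2 and overall rates are not on one scale. Imaging follows standard of care, so the modality mix may also differ between sites and between cohorts of six.

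**Working it through.** The plan gives no ORR target, power or precision, so there is no stated figure to reproduce. The check has two parts.

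**1. The texts side by side**

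| Place | Applies to | Cheson | Lugano |
|---|---|---|---|
| Table 3 footnote m | Period 1 | if CT | if PET/CT included |
| Table 5 footnote k | Period 2 | unconditional | unconditional |
| Table 7 footnote i | optional Cycle 2, both periods | unconditional | unconditional |
| Protocol 7.3.10 | all periods | cited | cited |
| SAP Section 6, best overall response | all subjects | named | named |
| Protocol 10.1.1.2, SAP 10.6.1 (secondary ORR) | full analysis set | required | not used |

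Footnote m is the only one of these that conditions Cheson on modality. Scoring does not need that condition: Appendix A has PET-based categories, for example "mass of any size permitted if PET negative" for a complete response.

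**2. Upper bound on the effect**

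Inputs:

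- Period 1 size of 30, the evaluable target in Protocol Section 3.3. This is the DLT-evaluable number, used here as a stand-in for the full analysis set.
- PET/CT share q: not in the documents, so varied from 0 to 100%.
- True ORR: not in the documents. Taken as 50%, with 30% and 70% as alternatives and the same in both modalities.

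Assumption for the bound: every PET/CT subject lacks a Cheson category and is counted as a non-responder. Then

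counted ORR = true ORR × (1 − q), with the denominator unchanged.

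At a true ORR of 50% (15 responders in 30), with Clopper-Pearson 95% intervals:

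| q | 15 × (1 − q) | Counted | 95% CI |
|---|---|---|---|
| 0% | 15 | 15/30 = 50.0% | 31.3–68.7% |
| 25% | 11.25 | 11/30 = 36.7% | 19.9–56.1% |
| 50% | 7.5 | 7/30 = 23.3% or 8/30 = 26.7% | 9.9–42.3% or 12.3–45.9% |
| 75% | 3.75 | 4/30 = 13.3% | 3.8–30.7% |
| 100% | 0 | 0/30 = 0% | 0–11.6% |

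At q = 50%, a true 9/30 (30%) gives 4.5, taken as 5/30 = 16.7%. A true 21/30 (70%) gives 10.5, taken as 11/30 = 36.7%.

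**By dose group.** In a cohort of six, one reclassified subject moves the rate by 1/6 = 16.7 percentage points.

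**Overall.** Assume the 54 enrolled subjects split as 30 × 1.2 = 36 in Period 1 and 15 × 1.2 = 18 in Period 2, with only Period 1 affected and a true ORR of 50% (27/54). At q = 50% the loss is 36 × 0.5 × 0.5 = 9, leaving 18/54 = 33.3%. At q = 100% the loss is 18, leaving 9/54 = 16.7%.

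If sites record both criteria, the loss is zero at every q.

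**The case against.** A reader might infer that the SAP turns every Period 1 PET/CT subject into a non-responder. The documents do not support that, for four reasons.

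- The rule in SAP 10.6.1 applies when no response assessment is available. A PET/CT subject with a Lugano category does have one. Treating it as missing is a plausible reading for a Cheson endpoint, but the SAP does not say so.
- Protocol Section 7.3.10 and the SAP definition of best overall response name both criteria, so a Period 1 site may well record both. The parenthesis in Section 7.3.10 could attach only to contrast-enhanced CT, but nothing there reserves Cheson for CT. Table 3's own footnotes n, o and s name both criteria for bone marrow.
- Table 7 footnote i covers Period 1 subjects who take optional Cycle 2 and asks for Cheson before that cycle and at end of study.
- Footnote m can be read as additive: Lugano is added when PET is included, and Cheson is not withdrawn.

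The CRF design is not in the documents. The stakes are also limited: efficacy is secondary and descriptive, no formal hypothesis is tested, and no ORR threshold drives a decision.

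All of this stands against a claim of certain bias, and it makes the (1 − q) formula a ceiling rather than an estimate. It does not remove the conflict. Sites have Period 1 instructions that can be followed in different ways, Table 7 helps only those who take Cycle 2, and the SAP is silent on a subject with a Lugano category alone.

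**Conclusion.** The inconsistency is established. Footnote m does not fit a Cheson ORR in the full analysis set, and it differs from the other places that describe response assessment. The consequence is possible rather than shown: a Period 1 PET/CT subject may have only a Lugano category, and may then be counted as a non-responder or entered under the wrong criteria.

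The size cannot be fixed from the documents. It ranges from no effect, if both criteria are recorded, to the upper bound of true ORR × (1 − share), which halves the Period 1 rate at a 50% PET/CT share. That bound rests on an assumed share, an assumed true ORR, no Cheson category for any PET/CT subject, and the strict reading of the non-responder rule. The point should be corrected because the remedy is cheap and the missing entries are best recovered before database lock.

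**What to change.** 1. **Table 3 footnote m.** Require a Cheson category (Appendix A) for every subject whatever the modality, with a Lugano category (Appendix B) added when PET/CT is used.
2. **Site queries.** Before database lock, ask sites for any missing Cheson category of Period 1 PET/CT subjects, assigned from scans already taken.
3. **SAP 10.6.1.** Keep all full analysis set subjects in the denominator. Define a non-responder under the missing-data rule as a subject for whom no Cheson category can be obtained after query. Report the number of subjects by modality and criteria.

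Merely exempting PET/CT subjects from the non-responder rule would not be enough, because it leaves them with no stated way to count in the denominator.

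The cost is one footnote, a short change to SAP 10.6.1, one count table and some CRF queries. No new scans are needed.
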